#### 2.5.2 Elimination Criteria and Substitution of subjects

#### 5.2.1 Elimination criteria

- Withdrawal of the FCI letter.
- Presentation of a serious adverse event related or not to the investigational product, which at the discretion of the PI and / or the sponsor could affect the patient's ability to continue with the study procedures safely.
- Non-tolerability or hypersensitivity to any of the compounds used during the tests (fluorescein, green lysamine, tetracaine).
- Non-tolerability or hypersensitivity to any of the drugs under investigation.

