#### 7.3 Outcomes Variables

#### 7.3.1 Primary outcome Variables

- Incidence of adverse events (AE) (Evaluation Time: day 8 and 10).
- Score of the Ocular Comfort Index (ICO) (TE: day 8).

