#### 7.3.3 Definition of variables, methods and scales to be used for their measurement

Variable	Туре	Unit (Symbol)	Method of measurement	normal value	evaluation time	statistical test
Primary						
Adverse events	Discreet	Number of cases (n)	Counting	0	VB, V1, VF y LLS	U de Mann- Whitney
events	Categoric al nominal	Present/ absent	Observation	Absent	LLS	χ2 or exact by Fisher
Score of	Discreet	Points	Questionnaire	NA	VB, VF	U de Mann- Whitney
Secondary						
MAVC	Discreet	Fraction	Poster of Snellen	1	VB, V1 y VF	U de Mann- Whitney
Corneal and conjunctival fluorescein staining	Ordinal	Levels	Direct observation with slit lamp and cobalt blue filter, Oxford scale graduation	0	VB, V1 y VF	χ2 or exact by Fisher
Corneal and conjunctival staining with lysamine green	Ordinal	Levels	Direct observation with slit lamp, Oxford scale graduation	0	VB, V1 y VF	χ2 or exact by Fisher
Conjunctiv al hyperemia	Ordinal	Normal / Very Mild / Mild / Moderate / Severe	Direct observation. Clasification of Efron.	Normal	VB, V1 y VF	χ2 or exact by Fisher
Chemosis	Categorical nominal	Present / absent		Absent	VB, V1 y VF	χ2 or exact by Fisher

Table 2. Defoperational definition of variables

The variables, the method and scales for their measurement are described in detail below. They are in order according to Table 2

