#### 8.4.3 Procedures for a serious adverse event

The AE care process considers the following stages:

[figure not shown]

Figure 4. Attention to the adverse event

During the development and conduct of the present study, undesirable harmful events or adverse reactions, of medical implication, may occur in the research subject, which do not necessarily have a causal relationship with PIs. These harmful phenomena can occur during the use of investigational drugs at authorized doses, for use in humans, by a local, national or international regulatory entity. However, the PI or the investigational drug may be suspected of causing some unwanted clinical

manifestation. AE, ADR or ARS to one or more medications can occur during the systematic evaluation of the participants (on the days when the clinical review is scheduled, according to the schedule of activities) or suddenly, in such a way that:

- 1. The researcher must be the first person to whom the patient notifies that he has developed or presented any harmful phenomenon of a clinical nature during his participation in this study.
- 2. According to her clinical judgment; Based on the pertinent physical examination, questioning, etc., as well as the analysis of the information available in the medical literature and what is referred to in the investigator's manual, Prescribing information, or the comparator drug's technical sheet, the principal investigator determines the relevant attention to the damaging event / reaction.
- 3. This care can be in the research center or in the hospital with the highest resolution power. In such a way that, in the event that the patient is sent by the IP to a hospital, he / she assists through a referral system. The referral can be with a card that identifies the subject as a study participant and links him to the pre-established agreement with the institution, or through a medical reference note issued by the IP. Laboratorios Sophia, S.A. de C.V., will pay the expenses for the medical care of the participating patient, when the adverse event is associated or is related to the PI or investigational drug.
- 4. Taking the clinical information collected, either during the care provided at the research center or that provided by the treating physician (s) at the hospital, the IP will record the AE in their clinical note, recording the seriousness, intensity (mild, moderate, or severe) and relationship to the investigational product or drug.

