#### 10.1.5 Subjects included in the analysis

Those subjects who comply with an adherence ≥75% will be included in the statistical analysis to fulfill the objective of the study, taken from the subject's diary.

The investigational drug will be considered safe and effective when there are no clinical and statistical differences in all the primary outcome variables, with respect to its comparator (Lagricel® Ofteno, unit dose).

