# 11.3 Early termination of the study

The study may be temporarily suspended or terminated prematurely if there is a sufficiently reasonable cause. The written notification, documenting the reason for the suspension or early termination, must be delivered by the party executing the suspension. The PI should promptly inform the study participants, the IC and the REC, providing the reasons.

Situations in which suspension or early termination of the study will be contemplated include, but are not limited to:

- 1. The presence of serious adverse events in more than 10% of the participants in a study group.
- 2. The regulatory authority (COFEPRIS) considered it for security alerts.
- 3. The Sponsor determined it for their convenience or eventualities such as: economic support, manufacturing errors, etc.
- 4. The determination of unexpected risks for participants, which are significant or unacceptable.
- 5. Obtaining new relevant safety information.
- 6. Insufficient adherence to the requirements of the protocol.
- 7. The data obtained are not evaluable or are not sufficiently complete.
- 8. The determination that the primary objective has been achieved.
- 9. The futility determination.

In case of suspension, the study can be resumed once the situations that led to the suspension have been corrected; as long as this justification is sufficient for the sponsor, CI, CEI and regulatory authorities.

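### The section 10.1.5 rule for calling the product safe uses only AE incidence and the ICO score, so an excess of serious or moderate/severe AEs can pass it

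*Combined protocol and SAP*

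**What the plan says.** - **The rule.** Section 10.1.5 calls the product safe and effective "when there are no clinical and statistical differences in all the primary outcome variables, with respect to its comparator". It does not say what a clinical difference is, and neither does any other section.
- **Its inputs.** Section 7.3.1 lists two primary variables: incidence of AEs, assessed at days 8 and 10, and the ICO score at day 8. Table 2 in section 7.3.3 scores AEs as a number of cases (Mann-Whitney) and as "Present/ absent" (chi-square or Fisher). It has no row for seriousness, intensity, relatedness or withdrawal.
- **What is recorded besides.** Section 8.4.3 has the investigator enter each AE, "recording the seriousness, intensity (mild, moderate, or severe) and relationship to the investigational product or drug". Section 8.3 grades intensity by consequence, from minimal symptoms needing no treatment up to events that need drug treatment and discontinuation. Section 5.2.1 lists as an elimination criterion "Non-tolerability or hypersensitivity to any of the drugs under investigation".
- **Early termination.** Among the situations in which section 11.3 would have suspension or termination considered is "The presence of serious adverse events in more than 10% of the participants in a study group". Section 10.1.5 does not refer to it.

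**The concern.** The trial's stated purpose is safety and tolerability, and the sentence in 10.1.5 is how that purpose is answered. Any-AE incidence is a blunt input for it. Section 7.3.3.1 expects mild sensations lasting no more than 30 seconds, and section 10.2.2 plans on an AE proportion of about 50%. In a present/absent table, a subject with brief burning counts the same as a subject with a severe or serious event.

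At stake is whether the conclusion can separate an arm whose AEs are all transient from an arm with a similar number of AE subjects, many of them moderate, severe or serious. The gap lies in the inputs. Changing the test, adding a margin on the same incidence or enlarging the sample would leave it in place.

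**Working it through.** The plan gives no figure of its own for how the rule behaves, so there is none to reproduce.

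**Inputs.** 17 subjects per arm (10.2.1); 50% of subjects with an AE in each arm (10.2.2); chi-square, or Fisher when an expected count is below 5 (10.1.2); Mann-Whitney for the ICO; α = 0.05. The documents give no moderate/severe share and no ICO shift, so those are assumptions.

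**1. The rule as a function.** *Safe* = no difference in AE count, and none in AE present/absent, and none in ICO.

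| Recorded item | Route into the rule |
|---|---|
| Seriousness, relatedness, intensity grade | None; the event counts as one AE |
| Elimination for non-tolerability | One AE; possible loss from the analysis set (step 4) |
| BCVA, staining, hyperemia, chemosis | One AE, only past the thresholds in 7.3.3.3 to 7.3.3.7 |
| Intensity of ocular symptoms | The six ICO symptoms, intensity scored 0 to 6 (annex 15.1) |

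**2. SAEs against the section 11.3 level.** 1/17 = 5.9% and 2/17 = 11.8%, so two subjects cross 10%. If these SAEs are the only AEs, the two-sided Fisher p for k/17 v 0/17 is 2·C(17,k)/C(34,k):

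| k | % | Fisher p | Mann-Whitney p |
|---|---|---|---|
| 2 | 11.8 | 2 × 136/561 = 0.485 | 0.163 |
| 3 | 17.6 | 2 × 680/5,984 = 0.227 | 0.080 |
| 4 | 23.5 | 2 × 2,380/46,376 = 0.103 | 0.039 |
| 5 | 29.4 | 2 × 6,188/278,256 = 0.044 | 0.018 |

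Two or three SAE subjects pass both planned AE tests; four pass Fisher only. With ordinary AEs also present the signal is diluted further: 8/17 v 8/17 AE subjects, two of the multi-dose cases serious, gives p = 1.00.

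**3. Moderate/severe AEs.** With 50% any-AE in both arms, the exact probability of a non-significant AE test is 0.942. With no ICO difference the rule is met in about 0.942 × 0.95 = 0.895 of trials, whatever the intensity mix. Let 5% of comparator AE subjects be moderate/severe (17 × 0.5 × 0.05 ≈ 0.4 expected). Let the multi-dose share be 100% (17 × 0.5 = 8.5 expected) or 50% (about 4.3 expected). Simulated probability that the rule returns *safe* **and** Fisher on moderate/severe AEs has p ≤ 0.05:

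| Multi-dose share | No ICO effect | ICO +1 SD in those subjects | ICO +2 SD |
|---|---|---|---|
| 100% | about 82% | about 65% | about 37% |
| 50% | about 27% | about 25% | about 20% |

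The simulation leaves out the Mann-Whitney test on AE counts; including it changes the results by about 1 percentage point.

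**4. Withdrawals.** Section 10.1.5 analyses subjects with at least 75% adherence: 0.75 × 28 = 21 applications, taking 4 a day for 7 days. Sections 6.4 and 10.1.3 keep low adherers and all exposed subjects in the safety analysis. As an illustration, 14/17 v 8/17 with an AE gives chi-square p = 0.031. Remove five multi-dose subjects who stopped early with AEs and 9/12 v 8/17 remains. The smallest expected count is then 4.97, so Fisher applies, p = 0.25. Losing intolerant subjects moves the result towards *safe*.

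**The case against.** Three stronger readings are tempting, and the documents support none of them.

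- *Severity and the secondary signs can never affect the conclusion.* They can, by limited routes. BCVA loss of more than two lines, corneal staining of grade III or above, hyperemia of grade 3 or above and any chemosis are handled as AEs and so add to incidence. The ICO asks about frequency and intensity of six ocular symptoms, which overlap with much of what the reference study in 10.2.2 reported. An assessor could also bring seriousness in through the word *clinical*. What remains uncovered is seriousness, relatedness, and the intensity grade of events that the ICO does not capture. An undefined word does not close that gap: it is tied to the primary variables and would be interpreted after the data are in.
- *Sections 10.1.5 and 11.3 contradict each other.* They do not strictly. Section 11.3 says stopping would be considered, not that it is automatic, and it governs conduct, not conclusions. Both can be followed. For that reason a trial can pass the 11.3 level, continue, and still be declared safe with nothing said about it.
- *82% estimates how often the rule would mislead.* It is a ceiling. It assumes an extreme split and no ICO effect. The two products share a formulation (2.2.4), and the expected AEs are mild.

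It can also be said that the final report will cover AEs anyway (8.4 and 13.1). That is true, but reporting them does not make them part of the stated conclusion.

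**Conclusion.** The point stands as a limitation of the decision rule. As written, 10.1.5 can return *safe* when serious or moderate/severe AEs are in excess on the multi-dose product, if AE incidence and ICO look alike. The SAE example (2/17 or 3/17 v 0/17; Fisher p = 0.48 or 0.23) is exact and needs only the planned 17 per arm and no ICO difference. The simulated figures rest on the assumed moderate/severe shares and ICO shifts, with 50% any-AE in both arms. They show how wide the gap could be and do not predict this trial. The data collection is sound; the conclusion rule should be amended before analysis.

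**What to change.** In section 10.1.5 and Table 2:

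- **(a) Intensity.** Classify each exposed subject by worst AE intensity (none, mild, moderate, severe) and compare arms by Mann-Whitney. Give the risk difference for any moderate or severe AE with an exact confidence interval. Require this comparison to show no difference, as for the other primary variables, before *safe* is concluded. At 17 per arm Fisher first reaches 0.05 at 5/17 v 0/17, so the interval should be read alongside the p-value.
- **(b) Clinical difference.** Define the term to include seriousness and relatedness. Reconcile 10.1.5 with 11.3: the sponsor should state how SAEs above the 11.3 level, or SAEs related to the product, bear on the conclusion.
- **(c) Non-tolerability.** Count these eliminations by arm, in all exposed subjects, within the same conclusion. Reconcile the 75% filter in 10.1.5 with sections 6.4 and 10.1.3.

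The cost is wording in 10.1.5 and one row in Table 2. Seriousness, intensity, relatedness and elimination reasons are already in the plan, so no extra subjects or visits are needed. Intensity must be graded consistently. There is one more comparison, and the claim becomes slightly harder to make: if the arms truly do not differ, one added test at 0.05 lowers the chance of concluding *safe* by at most about 5 percentage points.

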#### 10.2 Calculation of sample size

#### 10.2.1 Number of subjects calculated

n = 34 evaluable subjects (both eyes) 17 subjects per arm. 17 subjects (both eyes) are estimated per treatment arm.

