#### Study design:

Phase I, single-center, controlled, parallel-group, open-label, randomized clinical trial.

Number of subjects:	Main inclusion criteria:
n = 34 evaluable subjects	Clinically healthy subjects
17 evaluable subjects per group (both eyes).	

Study No: SOPH037-0119 / I

Sophia Laboratories, S.A. of C.V.

31-January - 2019

Version 1.0

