#### 2.4.3 Expected duration

The total duration of the study, from the first visit of the first patient to the preparation of the final report, is estimated to be 5 months.

The planned recruitment period is 3 months. Considering that the proposed sample is 34 subjects, the total average recruitment rate during the study should be no less than 0.37 subjects per day.

The approximate duration of each subject in the study is 10 days.

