#### 10.1.4 Deviations from the statistical analysis plan

According to the calculation of the sample size to meet the objective of the study, 34 evaluable subjects (17 subjects per arm / both eyes) are required. If this number is not met due to the loss of subjects greater than 20% contemplated in this protocol (loss of follow-up or withdrawal of ICF), in order to balance the treatment groups, the sponsor may substitute these subjects.

The results obtained from the substituted subjects will continue to be used for the safety analysis and will be part of the ITT.

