#### 10.2.2 Justification of the sample calculation

Although there are no references on the calculation of the sample size in phase I studies, it was considered pertinent to perform it according to the safety results of a phase I study, carried out with three ocular lubricants (Humylub Ofteno® PF, Xyel® Ofteno and Systane® Ultra). [53]

The reference study was a single-center, randomized, 1: 1: 1, parallel group, blinded clinical trial. In total, 30 ophthalmologically and clinically healthy subjects were enrolled and included in the safety analyzes.

PRO-037 (Lagricel® Ofteno, multi-dose) is expected to be not inferior to its comparator (Lagricel® Ofteno, single-dose), based on the following working hypotheses:

$$H_0: \varepsilon > \delta$$

$$H_0: \varepsilon \leq \delta$$

Where  $\mu A - \mu B = \epsilon$ , the true difference of the means between the test treatment (Lagricel® Ofteno, multi-dose) and the active control (Lagricel® Ofteno unit-dose). Where  $\delta$  is the margin of non-inferiority, and the relationship between the sample sizes of the two groups is given by:

$$k = \frac{n_A}{n_B}$$

The calculations were made using the equation for two proportions, considering a power of 80% ( $\beta$ ), a significance level of 0.05 ( $\alpha$ ) and a non-inferiority margin ( $\delta$ ) of 5%. [54]

$$n_B = (\frac{p_A(1-p_A)}{k} + p_B(1-p_B))(\frac{z_{1-\alpha} + z_{1-\beta}}{k})^2$$

$$p_A - p_B - \delta$$

In the reference study, after 10 days of treatment (1 drop / 4 times a day), 28 AE were reported in 14 subjects out of a total of 30 subjects exposed to any of the three interventions (46.67%). Without observing statistical differences in the incidence of AE between the three treatment arms (p = 0.788), 19 of the AE were ocular, where burning was the most common, followed by pruritus. Other ocular AE reported were discharge, SCE, and dry eye sensation.

The percentage of ocular AE reported in the study was considered, with respect to the total AE for the three treatments. As it is an ocular lubricant, a similar proportion of ocular AE is expected in ophthalmologically and clinically healthy subjects (50%).

The calculated sample was 56 eyes (28 eyes / arm; 14 subjects / arm), increasing the calculation by 20% considering possible losses, 17 subjects / arm (both eyes) are estimated.

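### The 34 subjects labelled evaluable are the 28 calculated plus the loss allowance, so the stated size and the substitution rule tied to it do not match the plan's own derivation

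*Combined protocol and SAP*

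**What the plan says.** - **Derivation (section 10.2.2).** "The calculated sample was 56 eyes (28 eyes / arm; 14 subjects / arm"), followed by the loss step: "increasing the calculation by 20% considering possible losses, 17 subjects / arm (both eyes) are estimated".
- **Stated size.** Section 10.2.1 has "n = 34 evaluable subjects (both eyes) 17 subjects per arm". The synopsis has "17 evaluable subjects per group (both eyes").
- **Stated requirement (section 10.1.4).** Citing the sample size calculation, it says that "34 evaluable subjects (17 subjects per arm / both eyes) are required".
- **Recruitment (section 2.4.3).** "Considering that the proposed sample is 34 subjects", the site must average at least 0.37 subjects per day over three months.
- **Substitution, first rule (section 10.1.4).** The condition reads "If this number is not met due to the loss of subjects greater than 20% contemplated in this protocol". The sponsor may then replace subjects who withdrew consent or were lost to follow-up. The text does not say whether the 20% is counted per arm or over the whole trial.
- **Substitution, second rule (section 5.3.1).** The sponsor may replace the same two kinds of subject where this is needed to keep the groups balanced and evaluable. No percentage is given, but prior ethics committee authorization is required. Section 10.1.4 does not mention that authorization.

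**The concern.** One number, 34, does two jobs that are compatible only if nobody is lost. In sections 10.2.2 and 2.4.3 it is the number brought into the trial, with losses already allowed for. In the synopsis and sections 10.1.4 and 10.2.1 it is the number that must remain after losses.

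The label matters for two reasons. A reader of the synopsis would credit the trial with six more analysable subjects than the calculation asks for (34 against 28). And the substitution rule in section 10.1.4 is written against the 34, so it inherits the confusion. The trial is open-label, the sponsor decides on replacement and the sponsor's own staff run the analysis, so the plan should fix in advance a single point at which replacement becomes available.

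**Working it through.** **Inputs.** Base size of 56 eyes, 28 eyes per arm, 14 subjects per arm; 20% loss allowance; 17 per arm after the allowance (all section 10.2.2). Recruitment of 34 at 0.37 per day over three months (section 2.4.3). Loss condition of more than 20% (section 10.1.4).

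**1. Reproduce the plan's figure.** 28 eyes / 2 = 14 subjects per arm. Then 14 × 1.20 = 16.8, rounded up to 17 per arm, 34 in total. Pooled, 28 × 1.20 = 33.6, again 34. The stated size is reproduced, and it is the size *after* the loss allowance. The evaluable number behind it is 2 × 14 = 28.

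**2. Check which 34 is recruited.** Taking three months as 92 days (an assumption), 34 / 92 = 0.370, the stated rate. With 90 days, 34 / 90 = 0.378. Either way the rate is built on 34 enrolled, with nothing added to deliver 34 evaluable.

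**3. Set the requirement against enrolment.** With 34 enrolled, one loss leaves 33, below the 34 that section 10.1.4 calls required. That loss is 1 / 34 = 2.9%, far from the 20% condition.

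**4. Find where the 20% condition is met.**

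| Reading | Losses | Percent | Remaining | Above 20%? |
|---|---|---|---|---|
| Per arm (17) | 3 | 17.6 | 14 | no |
| Per arm (17) | 4 | 23.5 | 13 | yes |
| Overall (34) | 6 | 17.6 | 28 | no |
| Overall (34) | 7 | 20.6 | 27 | yes |

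Per arm, the condition is first met exactly when an arm drops below 14, which agrees with section 10.2.2. Overall, six losses do not meet it, and all six could fall in one arm: 17 − 6 = 11 there, three below the calculated 14, with no substitution available under section 10.1.4.

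**5. Check the inflation step (secondary).** To expect *n* evaluable after a loss fraction *d*, enrol *n* / (1 − *d*): 14 / 0.8 = 17.5, so 18 per arm. The plan used *n* × (1 + *d*), giving 17. Expected evaluable at exactly 20% loss: 17 × 0.8 = 13.6; 18 × 0.8 = 14.4. The gap is one subject per arm.

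**6. Exclusions outside both rules.** Section 10.1.5 drops subjects below 75% adherence from the main analysis. They reduce the evaluable number, but neither substitution rule covers them.

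**The case against.** The strongest defence is that this is a labelling slip around a workable plan, and much of that stands.

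- **The trigger does not contradict the calculation.** A reader might infer that the 20% rule conflicts with 14 per arm. Read per arm, it does not: it is met at four losses of 17, the first point at which fewer than 14 remain. It conflicts only with the statement that 34 evaluable are required.
- **Section 10.1.4 does not allow replacement after one loss.** It sets a single compound condition, a shortfall *caused by* loss above 20%, and one loss of 34 does not meet it. The looser rule is in section 5.3.1, and that one needs ethics committee authorization.
- **The allowance is not too small in whole subjects.** Any per-arm loss of up to 20% means at most three of 17, which leaves 14. The 13.6 is an average, not an attainable count.
- **Retention probabilities prove little.** If each subject is lost independently with probability 20% and nobody is replaced, both arms keep at least 14 with probability 0.30. Starting from 18 per arm, the figure is only 0.51, so the calculation mostly reflects random variation in losses. It also ignores the substitution that the plan allows.
- **Losses matter less for the adverse event outcome.** Section 10.1.3 keeps every exposed subject in the safety analysis, and section 10.1.4 keeps replaced subjects there.

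What the defence does not answer is that three places call 34 evaluable, one of them attributes that requirement to a calculation that gives 28, and two sections give different substitution rules, one without a threshold and the other without saying what its threshold is a percentage of.

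**Conclusion.** Wrong as written, in a limited way. The plan's own derivation gives 28 evaluable subjects (14 per arm) and 34 to randomise. The synopsis and sections 10.1.4 and 10.2.1 mislabel the 34, overstating the evaluable number by six, and as worded the requirement fails at the first loss. The substitution rules need one reading: under the overall reading of section 10.1.4, an arm could fall to 11 with no remedy there. The multiply-for-divide slip is real but worth one subject per arm.

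The documents do not support the view that the trial must enrol more. If 34 evaluable were truly required, 17 / 0.8 = 21.25 would mean 22 per arm, 44 in total, but neither section 10.2.2 nor the recruitment target points that way.

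The conclusion assumes equal arms and takes 14 per arm as the protocol's figure. Whether 14 follows from the declared proportion, margin, significance level and power is a separate problem, and nothing here endorses that number.

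**What to change.** 1. **Synopsis, 10.1.4 and 10.2.1:** replace the evaluable wording with: *34 subjects randomised (17 per arm), allowing for losses from the protocol's calculated 14 evaluable per arm*.
2. **10.2.2:** state that 17 per arm tolerates up to three losses per arm (17.6%), not a full 20%.
3. **10.1.4 and 5.3.1:** state one replacement trigger in both, counted per arm and set against the calculated evaluable number, keeping the ethics committee authorization. Say whether subjects excluded for low adherence count towards it.

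The cost is wording in five places. Enrolment and the recruitment target do not change. The stated evaluable size becomes less favourable, from 34 to 28.
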